12.1. ADVERSE EVENTS

AEs will be coded using MedDRA version 23.1.

AEs will be considered treatment-emergent (TE) unless there is a clear indication that the event occurred prior to the first administration of study drug. AEs with missing start dates will be taken as TE unless the end date occurs before Day 1. If there is a partial start date, then the AE will be taken as TE unless suggested otherwise by the partial information provided and the end date.

Any AEs reported prior to dosing in either REN001-201 or REN001-202 (for subjects enrolling at REN001-201 Exit, from REN001-101 or nDNA-PMM subjects) will be reported as pre-treatment AEs in the databases and will therefore not be reported as TE (checks will be made of the AE start date against the start of dosing). Subjects who receive placebo in REN001-201 will have their TE events reported in REN001-201 assigned to placebo. Any events that are ongoing at the start of REN001-202 will only be assigned to mavodelpar if they worsen in severity on or after the start of dosing in REN001-202.

Note, any ongoing AEs at the end of REN001-201 for subjects enrolling at REN001-201 W24 or REN001-201 FU will be recorded on the pre-treatment AE eCRF page for REN001-202; if the event resolves during REN001-202 the record will be updated. These events will be considered TE to the REN001-201 treatment.

If an adverse event has a missing start date where the stop date is after the dosing date, or missing, the date will be imputed as the dosing start date and for a missing start date where the stop date is before the start date of dosing, the date will be imputed as the day of informed consent and classified as a pre-treatment AE; for a missing stop date the TEAE will be considered as ongoing at the last visit date. If a partial date is recorded, the following convention will be used to assign the AE based on the database that the AE was recorded in:

- If a start date is missing the day information and month/year is the same as the dosing start date then use the dose start date, else '01' will be used for the day; if a start date is missing the day/month and the year is the same as the dosing start date then use the dose start date, else January will be used for the start month.
- If a stop date is missing the day information and month/year is same as last study date then use last study date, else last day of the given month will be used for the stop day; if a stop date is missing the day/month and year is the same as last study date then use last study date, else December will be used for the stop month.

Only TEAEs will be included in the summary tables. Summaries will be generated for all TEAEs. Summaries will be presented overall and split by time period looking at AEs reported (based on AE start date) in the first month (up to and including Day 28), 2-6 months (Day 29 to Day 168 inclusive), 6-12 months (Day 169 to Day 336 inclusive) and >12 months (after Day 336). Summaries will be repeated for the subgroups – age (<65 years or ≥65 years), sex and race.

An overall summary will present the number and percentage of subjects with:

- any TEAE
- any TEAE considered as related to study drug (evaluated by the investigator as Possibly Related or Related)
- any TESAE
- any TESAE considered as related to study drug
- any AESI
- maximum severity TEAE of mild, moderate, or severe; i.e. a subject with TEAEs at different intensities will be summarized at the most severe intensity
- maximum severity for TEAE considered as related to study drug
- any TEAE leading to study drug discontinuation
- any TEAE leading to death

The table will include the total number of TEAEs reported. The total number of unique terms within subjects will also be presented, counting each TEAE PT only once within each subject.

The number and percentage of subjects with TEAEs will be presented by System Organ Class (SOC) and PT. Subjects with multiple TEAEs within a SOC or SOC/PT combination will be counted only once for that SOC or SOC/PT combination. Similar summaries will be presented for related TEAEs, AESI and TESAEs.

SOC and PT summaries of TEAEs by maximum severity (mild, moderate or severe) will be presented.

All summaries will be ordered by descending frequency of total number of subjects within each SOC and then similarly by decreasing frequency of total number of subjects within each PT, in the REN001 treatment group (i.e., from start of REN001-201 and from start of REN001 treatment this will be the REN001 100 mg group, and from start of REN001-202 this will be the mtDNA PMM Overall REN001 100 mg group). In cases of SOCs or PTs with equal frequencies, AEs will be sorted alphabetically.

All AEs will be listed with their onset and end study days. AE duration (stop date/time – start date/time or [stop date – start time + 1] for AEs with no time information) will be included in the listing for those AEs no longer ongoing; where applicable imputed data will be used for the calculation of AE duration, but the original date/time information will be presented in the listing. For ongoing AEs the duration will be calculated using the last contact date and presented with a prefix of ‘>’ to indicate it is an estimate. The listing will identify treatment emergent AEs, AESI and SAEs. The associated study (REN001-201 and REN001-202) of AE onset and the assigned treatment emergence period (pre-treatment, REN001-201 or REN001-202) will also be listed.

A separate listing of TESAEs, TEAESI and TEAEs leading to study drug discontinuation will also be generated. If there are any deaths a listing will include the date of death and the adverse event(s) associated with death.

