7.1.1.4 Worsening of PTEs and AEs

If the subject experiences a worsening or complication of PTE or an AE after starting the study drug in this study, the worsening or complication should be recorded as a new AE. Investigators should ensure that the AE term recorded captures the change in the condition (e.g., "worsening of...").

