7.1.1.6.2 Severity

The intensity of each AE must be assessed by the Investigator using one of the following categories, and recorded in the eCRF:

- Mild: An AE that does not interfere with usual activities.
- Moderate: An AE that interferes with usual activities.
- Severe: An AE that prevents usual activities.

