3.2. STUDY ENDPOINTS

3.2.1. Primary Endpoints

- Number and severity of Adverse Events (AE)
- Number of AEs leading to study drug discontinuation
- Number of serious adverse events (SAE)
- Number of adverse events of special interest (AESI)
- Number of AEs leading to death

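### An AE that began on placebo, carries over at unchanged severity and makes the subject stop mavodelpar is left out of the mavodelpar discontinuation counts

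*SAP*

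**What the plan says.** SAP 12.1 handles AEs still open at a Week 24 or follow-up roll-over in four steps.

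- Recording: such an event "will be recorded on the pre-treatment AE eCRF page for REN001-202".
- Default attribution: "These events will be considered TE to the REN001-201 treatment". For the placebo arm this means: "Subjects who receive placebo in REN001-201 will have their TE events reported in REN001-201 assigned to placebo".
- The only route to mavodelpar: "Any events that are ongoing at the start of REN001-202 will only be assigned to mavodelpar if they worsen in severity", with the worsening falling on or after the first REN001-202 dose.
- Tabulation: "Only TEAEs will be included in the summary tables". In the overview table, the rows for discontinuation, serious events and death are all limited to treatment-emergent events.

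The primary endpoints in SAP 3.2.1 include "Number of AEs leading to study drug discontinuation". Protocol 3.2.1 lists the same endpoint.

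Two protocol rules also bear on the point. Protocol 7.1.1.4 says that if a pre-treatment event or AE worsens or becomes complicated after study drug is started, "the worsening or complication should be recorded as a new AE". Protocol 7.1.1.6.2 uses a three-level severity scale whose top level is "Severe: An AE that prevents usual activities".

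**The concern.** Whether an AE led to stopping drug does not depend on whether its grade rose. An AE can persist at a constant grade until the subject decides to stop. SAP 12.1 makes a rise in grade the only trigger that moves a carried-over event to mavodelpar, and it has no rule for an unchanged event that ends treatment.

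At stake is a primary-endpoint count in a study whose primary objective is long-term safety and tolerability. The omission runs in one direction: it can only lower the number of discontinuations shown for mavodelpar. It can also make two tables disagree. Protocol 3.6 tells sites not to record an AE withdrawal as voluntary, and SAP 9.1 tabulates withdrawal reasons without reference to treatment emergence. Disposition could therefore show an AE withdrawal that has no counterpart in SAP 12.1.

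**Working it through.** The plan has no calculated figure to reproduce: no testing is planned and the sample size has no statistical basis. The check is to apply the rules to each case.

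**Step 1. Does another rule catch the event?** Take a moderate AE that began on placebo, is still moderate, has no complication, and leads the subject to stop mavodelpar.

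- Protocol 7.1.1.4 does not apply. Stopping drug for an unchanged event is neither a worsening nor a complication, so no new AE is created.
- The TEAE definition in Protocol 7.1.1.1 does not apply. It needs onset, or a rise in severity, after the first dose.
- The same holds for an event already graded severe, which has no higher grade to move to.

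**Step 2. Which presentation counts the discontinuation?**

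| REN001-201 arm | Carried-over AE | Start of REN001-202 | Start of REN001 |
|---|---|---|---|
| Placebo | Grade unchanged, no new AE record | Not counted | Not counted |
| Placebo | Grade rises, or new AE under 7.1.1.4 | Counted | Counted |
| Mavodelpar | Grade unchanged, no new AE record | Not counted | Counted |
| Mavodelpar | Grade rises, or new AE under 7.1.1.4 | Counted | Counted |

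The first row is the gap. The third row affects one presentation only, because the event was already treatment-emergent to mavodelpar in REN001-201.

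**Step 3. Serious and fatal outcomes.** An AE that turns serious or fatal would normally be a worsening or complication, hence a new AE with onset after the first dose. It is lost only if the site updates the old record instead. SAP 12.1 does not refer to Protocol 7.1.1.4, so it leaves open how the two rules fit together.

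**Step 4. Scale of one missed event.** Group size n is an assumption, because the documents do not give the placebo share. The exact 95% upper limit for x events is the 0.975 quantile of Beta(x + 1, n − x).

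| n (assumed) | Shown: 0 events (upper limit) | True: 1 event (upper limit) |
|---|---|---|
| 50 | 0% (7.1%) | 1/50 = 2.0% (10.7%) |
| 75 | 0% (4.8%) | 1/75 = 1.3% (7.2%) |
| 100 | 0% (3.6%) | 1/100 = 1.0% (5.5%) |

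**Step 5. How many events?** The documents give no rates. As an illustration only, assume 75 ex-placebo subjects (half of the estimated 150 mtDNA subjects), 10% to 20% with an AE open at roll-over, and 5% to 10% of those stopping because of it. The low end is 75 × 0.10 × 0.05 = 0.375 and the high end is 75 × 0.20 × 0.10 = 1.5. All three inputs are assumed. The base of 75 is if anything too large, since the 150 also covers REN001-101 subjects and those who enrol after exiting REN001-201.

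**The case against.** The strongest defence is that the SAP applies the protocol's own TEAE definition, which uses onset or a rise in severity, and that Protocol 7.1.1.4 complements it. One rule creates a new record for a change and the other governs the old record. Nothing is hidden either: SAP 12.1 lists every AE with its study of onset and its treatment-emergence period, deaths have their own listing, and disposition shows withdrawal reasons.

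Much of this stands, and it rules out three stronger readings that a reader might infer.

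- *Serious events and deaths on mavodelpar are generally undercounted.* The documents do not support this, because Protocol 7.1.1.4 would normally produce a new, treatment-emergent AE.
- *These events are charged to placebo in the start-of-REN001-201 table.* Under SAP 2 and 8.2 the columns of that table are the REN001-201 treatment groups, followed through open-label treatment. An ex-placebo subject's later events fall in that column by design, whatever the carry-over rule.
- *Events in subjects on mavodelpar in REN001-201 are lost to mavodelpar.* They remain in the start-of-REN001 presentation, which SAP 2 singles out as particularly relevant to safety.

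The defence does not answer the discontinuation case. Following the TEAE definition is what produces the omission, Protocol 7.1.1.4 does not reach an unchanged event, and a listing does not correct a summary count of a primary endpoint.

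**Conclusion.** The point holds in a narrow form. A stated rule gives an incomplete count of AEs leading to discontinuation of mavodelpar. It affects ex-placebo Week 24 and follow-up enrollers in two presentations, and ex-mavodelpar enrollers in the start-of-REN001-202 presentation only. Serious and fatal outcomes are exposed only if a site updates the old record rather than entering a new AE.

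The number of affected subjects cannot be derived from the documents and is probably small; the range in Step 5 reflects its assumptions and is not an estimate. The direction is known, however, and favours mavodelpar. If discontinuations for AEs are few, one omission changes the picture visibly, as Step 4 shows. The SAP should be amended before database lock. Sample size and trial conduct are unaffected.

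**What to change.** Leave the protocol's TEAE definition as it is. In SAP 12.1:

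1. Add rows to the start-of-REN001-202 and start-of-REN001 overviews, with matching listing flags, for any AE, including a carried-over one, that leads to mavodelpar discontinuation, leads to death or becomes serious, whatever its onset date. The outcome must fall on or after the first REN001-202 dose, or the first mavodelpar dose for the start-of-REN001 presentation.
2. Label these rows as not restricted to TEAEs, so that a subject who appears there but not under any TEAE is not read as an error.
3. Count each subject once where Protocol 7.1.1.4 has already produced a new AE, and cross-refer to that section.
4. Reconcile the discontinuation row with the AE withdrawals in SAP 9.1.

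The cost is SAP wording and one extra derivation. Protocol 7.1.1.8.2 already collects the action taken with study drug, the outcome and the seriousness of each pre-treatment event and AE. The downside is that mavodelpar counts may become slightly less favourable.

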7.1.1.8.2 PTE and AE Reporting

AEs at the end of the STRIDE study for subjects enrolled at the STRIDE Week 24 or FU visits that are still present at the time the subject signs the informed consent to participate in this study should be followed up in this study and recorded in the eCRF as PTEs.

At each study visit, the Investigator will assess whether any subjective AEs have occurred. A neutral question, such as “How have you been feeling since your last visit?” may be asked.

Subjects may report AEs occurring at any other time during the study.

All subjects experiencing AEs, whether considered associated with the use of the study drug or not, must be monitored until the symptoms subside and any clinically relevant changes in laboratory values have returned to baseline or until there is a satisfactory explanation for the changes observed. All PTEs/AEs will be documented in the PTE/AE page of the eCRF, whether or not the Investigator concludes that the event is related to the study drug. The following information will be documented for each event:

- Event term
- Start and stop date {and time}
- Severity
- Investigator’s opinion of the causal relationship between the event and administration of study drug
 - If no, provide alternative aetiology or explanation
- Investigator’s opinion of the causal relationship to study procedure(s), including the details of the suspected procedure
- Action concerning study drug
- Outcome of event
- Seriousness.

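### AEs with no start date, or only the dosing year, are imputed to the dosing start date, and the time-period tables then count them in the first month whatever their true onset

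*SAP*

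**What the plan says.** SAP 12.1 sets these rules for an incomplete AE start date:

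- Wholly missing: "missing start date where the stop date is after the dosing date, or missing, the date will be imputed as the dosing start date".
- Year only: "if a start date is missing the day/month and the year is the same as the dosing start date then use the dose start date". For any other year the fallback reads "else January will be used for the start month".
- Which dosing date applies to a partial date: "the following convention will be used to assign the AE based on the database that the AE was recorded in". The section gives no matching statement for a wholly missing date.

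An AE without a start date counts as treatment-emergent unless its end date precedes Day 1, so it enters the summary tables. Those tables are shown as a whole and also "split by time period looking at AEs reported (based on AE start date) in the first month (up to and including Day 28"), then "2-6 months (Day 29 to Day 168 inclusive), 6-12 months (Day 169 to Day 336 inclusive) and >12 months (after Day 336"). There is no row for unknown onset and no sensitivity table.

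Apart from classifying the event, the one use that the section names for imputed dates is the AE listing: "where applicable imputed data will be used for the calculation of AE duration, but the original date/time information will be presented in the listing".

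Protocol 7.1.1.8.2 has AEs assessed at every study visit and offers "How have you been feeling since your last visit" as a question that may be put to the subject.

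**The concern.** Taking the earliest possible date is right for deciding whether an undated event could have arisen on treatment. It is a poor answer to a different question, namely when the event began. The period tables ask that second question, and an event without a start date has no other date by which to be placed.

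The primary objective is long-term safety, and the period split is the only AE summary by time on drug described in SAP 12.1. An error that always moves onset earlier adds to the first month and takes from the later periods. After Month 6 the visits are six months apart (apart from the two extra German visits), so onset dates become harder to recall just where the long-term information is collected.

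**Working it through.** The plan states no figure on this point, so there is none to reproduce.

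**1. Inputs.** The period limits are Days 28, 168 and 336 (SAP 12.1), and the last scheduled visit is Day 1344 (Protocol 6.13). The periods therefore last 28, 140, 168 and 1008 days. The share of AEs with no start date, *f*, is not given; 0.5%, 1% and 2% are assumed. A flat AE rate over full follow-up is also an assumption.

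**2. One event.** A subject is seen at Month 30 (Day 840) and Month 36 (Day 1008), and an AE with no start date is first reported at Month 36. The rule gives Day 1, so the event is counted in the first month. If it was absent at the Month 30 review, its true onset lies in Days 841 to 1008, in the period after 12 months. The displacement is at most 1008 − 1 = 1007 days.

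**3. Wholly missing dates, tables from the start of REN001-202.** Under a flat rate the true shares are 28/1344 = 2.1%, 140/1344 = 10.4%, 168/1344 = 12.5% and 1008/1344 = 75.0%. With *p* the true first-month share, the tabulated first-month share is (1 − *f*)*p* + *f*. The tabulated share after Day 336 is (1 − *f*) × 75.0%.

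| *f* | First month, *p* = 2.1% | After Day 336 | First month if *p* = 10% |
|---|---|---|---|
| 0 | 2.1% | 75.0% | 10.0% |
| 0.5% | 2.6% | 74.6% | 10.5% |
| 1% | 3.1% | 74.3% | 10.9% |
| 2% | 4.0% | 73.5% | 11.8% |

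**4. Year-only dates.** The rule was applied to every dosing date in one calendar year combined with every onset day from 1 to 1344, reading January as 1 January. Each row shows where events of that true period are placed:

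| True onset | First month | Day 29–168 | Day 169–336 | After Day 336 |
|---|---|---|---|---|
| Day 29–168 | 80.7% | 19.3% | 0 | 0 |
| Day 169–336 | 38.5% | 38.4% | 23.2% | 0 |
| After Day 336 | 0.4% | 4.8% | 12.8% | 81.9% |

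Only 13.6% of year-only events have their onset in the dosing year and so go to Day 1. In all, 31.6% move to an earlier period, and no imputed date falls after the true onset. For dosing on 1 July, an event dated only to the next year goes to Day 185, and one dated to the year after goes to Day 550. A later-year date reaches the first month only if dosing began on 5 December or later, when 1 January is Day 28 or earlier.

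**5. Combined presentations.** For a mavodelpar subject continuing from REN001-201, Day 1 of REN001-202 is about Day 168 + 1 = 169 for entry at Week 24. For entry at follow-up, 21 to 28 days after the last dose (SAP Appendix 2), it is about Day 168 + 21 + 1 = 190 to Day 168 + 28 + 1 = 197. If the REN001-202 dosing date applies, an undated REN001-202 event falls in the 6–12 month period. If the REN001-201 date applies, it falls in the first month. The SAP does not say which applies to a wholly missing date.

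**The case against.** The strongest case against is that few events will be affected and that nothing primary depends on them.

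- Start and stop dates are to be recorded for every event (Protocol 7.1.1.8.2). Data queries (Protocol 9.2 and 9.4) and a review before lock (Protocol 8.1.3) follow. SAEs are reported within 24 hours and AESIs in the same manner, so a late SAE or AESI with no start date is unlikely. This stands, and it argues for a low *f*. It does not remove the point, since the SAP itself provides a rule for such events.
- The primary endpoints carry no time split, no test is planned, and the listing shows the original dates. This stands in full.
- The tables give numbers and percentages of subjects, each counted once per SOC or preferred term, so a misplaced event changes nothing for a subject already counted in that cell. This also stands: the event shares above are a guide to scale and do not predict the tabulated percentages.
- SAP 12.1 does not state that the imputed date drives the period split. That is an inference, though a near-certain one, because the section offers no other way to place the event.
- A lower bound from the previous visit is not always available. The AE items listed in Protocol 7.1.1.8.2 do not include the visit of first report, the neutral question is optional, and subjects may report events between visits. This stands and shapes the fix.

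**Conclusion.** The point holds as a narrow flaw in a descriptive table. Followed as written, the rule puts every wholly undated AE, and every AE dated only to the dosing year, in the first month of the tables from the start of REN001-202. The time-period split and the listed AE duration are affected, always towards an earlier onset. Overall TEAE counts are not affected.

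The size rests on an assumed *f* and a flat AE rate. At 1% wholly undated, the first-month share is 3.1% in place of 2.1%, and the share after Day 336 is 74.3% in place of 75.0%.

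A reader might infer two stronger things that the documents do not support. One is that all year-only dates collapse to Day 1. The January rule prevents that: 0.4% of true onsets after Day 336 reach the first month, and 81.9% stay in their own period. The other is that long-term use would look materially safer. Under the flat-rate model the relative loss from the last period equals *f* itself, here 0.5% to 2%. The first-month share looks strongly inflated only because its base is 2.1%.

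**What to change.** 1. Keep the current imputation for the treatment-emergent flag only.
2. In the period tables, add an onset-date-unknown row. Use it for events whose known information (partial start date, stop date and, where held, the visit of first report) does not fix a single period. Footnote the number. Many later-year dates would stay where they are: with dosing on 1 July, any onset from the second following year is Day 550 or later and belongs after 12 months.
3. In the listing, mark an AE duration built on an imputed start as an upper estimate. For an ongoing event, which already carries a > prefix, flag the start as imputed, because the prefix then no longer signals a minimum.
4. State which study's dosing start date applies to a wholly missing date in the combined REN001-201 and REN001-202 presentations.

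The cost is a few lines of SAP text and code and one extra table row. SAP section 2 allows amendments before database lock.
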